6.6 Analysis of Virus Variants

SARS-CoV-2 viral genome sequence analysis will be performed using Next Generation Sequencing (NGS) using the ARTIC primers/protocol on Illumina platform to evaluate the presence polymorphisms and genetic variations on the amino acid level.

Sequence results will be presented only for the spike protein. The assignment of approximate lineages is based on the predefined set of S amino acid substitutions agreed with the known circulating lineages based on the GISAID database (<https://www.gisaid.org/>) and the CDC guidelines (<https://www.cdc.gov/coronavirus/2019-ncov/cases-updates/variant-surveillance/variant-info.html>).

The SARS-CoV-2 Variant of Concern (VOC) and the SARS-CoV-2 variants of Interest (VOI), listed on the timing of database lock, will be included in the analysis.

6.6.1 Time Points and Samples

Samples for viral sequencing are taken throughout the protocol Time&Event schedule, but sequencing is triggered at the discretion of the virologist considering the SARS-CoV-2 viral load levels and the limitations of the sequencing assays. By preference, the screening/baseline sample is selected. If the viral load of this sample is below the limit of detection of the sequencing assay, another sample as close as possible to the baseline timepoint, is selected.

For the statistical analysis, results from all available samples will be considered and data will not be reported by timepoint.

6.6.2 Definitions

Polymorphisms, ie genetic variations, are defined as amino acid changes from the SARS-CoV-2 Wuhan-Hu1 Reference Sequence.

Wild type: If at certain position the amino acid in the participant sequence matches the reference sequence, that is no genetic variation is present at that position, the virus is considered to be wild type at that position.

6.6.3 Parameters to Analyze

The following parameters will be analyzed:

Number (%) of participants with a specific virus variant specific substitution profile.

SARS-CoV-2 Virus Variants:

To classify SARS-CoV-2 S sequences into their most probable lineages the following predefined substitution profiles were used:

| Variant Name | Spike Protein Substitutions | First Detected |
|------------------|---|----------------------------|
| B.1.526 | T95I, D253G, D614G | United States (New York) |
| B.1.526.1 | D80G, Δ144, F157S, L452R, D614G, D950H | United States (New York) |
| B.1.525 | A67V, Δ69/70, Δ144, E484K, D614G, Q677H, F888L | United Kingdom/Nigeria |
| P.2 | E484K, D614G, V1176F | Brazil |
| B.1.1.7 | Δ69/70, Δ144, N501Y, A570D, D614G, P681H, T716I, S982A, D1118H | United Kingdom |
| P.1 | L18F, T20N, P26S, D138Y, R190S, K417T, E484K, N501Y, D614G, H655Y, T1027I | Japan/Brazil |
| B.1.351 | D80A, D215G, Δ241/242/243, K417N, E484K, N501Y, D614G, A701V | South Africa |
| B.1.427 | L452R, D614G | United States (California) |
| B.1.429 | S13I, W152C, L452R, D614G | United States (California) |
| B.1.617 | L452R, E484Q, D614G | India |
| B.1.617.1 | G142D, E154K, L452R, E484Q, D614G, P681R, Q1071H | India |
| B.1.617.2 | T19R, Δ156, Δ157, R158G, L452R, T478K, D614G, P681R, D950N | India |
| B.1.617.3 | T19R, G142D, L452R, E484Q, D614G, P681R, D950N | India |

6.6.4 Analysis Methods

Frequencies and percentages will be presented for the variants detected. The denominator is the number of participants with sequencing data. Summaries will be provided by subgroup and intervention arm. Subgroups will be:

- Baseline CRS score (<=3, <=4, 4, 5)
- Center (US10006 and US10033, other)

Tabulation to investigate how the virus variants are spread during the entire study duration will also be provided.

7 BIOMARKERS

7.1 General

The biomarkers will be analysed using AST and Primary analysis sets.

The biomarkers are measured at scheduled visits during the study as mentioned in the protocol.

A table in section 7.2 below provides the list of biomarkers included for the analysis.

7.2 Data Handling Rules

Missing values will not be imputed and not used for the analysis. The measurements below the LLOQ will be imputed as LLOQ/2, and measurements above ULOQ by ULOQ.

In case measurements are not observed exactly on the scheduled days as per protocol, the measurements from adjacent days as shown below (as Measurement Day) may be used for the analysis. The measurement closest to the analysis day will be used. In case there are two measurements equidistant from the analysis day then the later of the two measurements will be used for the analysis of different biomarkers, the table below provides the analysis day (target day) and the corresponding study days of measurements to be included in the windows.

| Biomarker (Central lab) | Study Days of Measurements | Analysis Day (Target Day) |
|---|----------------------------|---------------------------|
| CRP | 2, 3 | 3 |
| D-Dimer | | |
| Pro-calcitonin | 4, 5, 6 | 5 |
| Serum Ferritin | 7, 8, 9 | 7 |
| | 12 to 16 | 14 |
| | 19 to 23 | 21 |
| | 26 to 30 | 28 |
| Cytokines | 4 to 6 | 5 |
| • Interferon Gamma | | |
| • Interleukin 1 Beta | 12 to 16 | 14 |
| • Interleukin 2 | | |
| • Interleukin 4 | 19 to 23 | 21 |
| • Interleukin 8 | | |
| • Interleukin 10 | 26 to 30 | 28 |
| • Interleukin 12p70 (or Interleukin 12) | | |
| • Interleukin 13 | | |
| • Tumor Necrosis Factor (or TNF-Alpha) | | |
| Chemokines | | |
| • Eotaxin-3 (or CCL26) | | |
| • IP-10 (or IFNGIP10 or CXCL10) | | |

| Biomarker (Central lab) | Study Days of Measurements | Analysis Day (Target Day) |
|--|--|---------------------------|
| 
 • Macrophage Inflammatory Protein 1 Alpha (or CCL3) • Macrophage Inflammatory Protein 1 Beta (or CCL4) • Monocyte Chemotactic Protein 1 (or CCL2) • Monocyte Chemotactic Protein 4 (or CCL13) • Macrophage-Derived Chemokine (or CCL22) • TARC (or CCL17) | | |
| Free IL-6 | 12 to 16 | 14 |
| Total IL-6 | 19 to 23 | 21 |
| | 26 to 30 | 28 |
| SARS-CoV-2 Ab (IgA, IgG, IgM) | 5 to 9 12 to 16 19 to 23 26 to 30 | 7* 14 21* 28 |

* No samples are scheduled on these days, but window may include unscheduled visits or final visit.

7.3 Analysis Methods

7.3.1 Analysis of Biomarkers

Over time tables and plots will show the results at target days.

The baseline values of biomarkers will be summarized (see Section 4.1 for more details).

Biomarkers will be summarized over time showing n, Geometric Mean, SE of Geometric Mean, Median, IQR, Minimum, and Maximum. For post-baseline visits, tables will include descriptive statistics (n, Mean, SE, Median, Tertiles, IQR, Minimum, and Maximum) for ratio (visit value/baseline value). Box plots of values over time will be provided displaying the actual values (using \log_2 scale on Y-axis) and presenting the geometric mean values. Box plots for ratio of visit value/baseline value ($\log_2(\text{visit value} / \text{baseline value})$) over time will also be generated.

7.3.2 Analysis of SARS-CoV-2 Antibodies (Ab)

For each SARS-CoV-2 antibodies (IgA, IgG, IgM) a stacked bar chart with percentage of subjects with positive, negative or borderline results over time will be presented. Time points will be those as defined in section 7.2.

8 PHARMACOKINETICS (PK) AND IMMUNOGENICITY (IMG)

8.1 General

As mentioned earlier in section 2.2 of the SAP, the Pharmacokinetics (PK) analysis set includes all participants in the AST analysis set with no interruption of study medication and who also had

at least 1 valid blood sample drawn for PK analysis after dose of Sirukumab. The PK analysis will be performed using the PK analysis set and will exclude any participant who received the Placebo. The PK concentration of Sirukumab is evaluated pre- and post-dose on Day 1 and at Day 14, 21 and 28.

Serum samples to evaluate the antibodies to Sirukumab are collected on Day 1 pre-dose and on Day 28. As mentioned in section 2.2 the Immunogenicity (IMG) analysis set consists of participants in AST analysis set who received a dose (full or partial) of Sirukumab during the study and have at least one valid blood sample for immunogenicity analysis after Sirukumab dose, and will exclude any participant who received the placebo. This analysis set will be used to analyze immunogenicity using the actual treatment received by a participant (IMG analysis set as Treated).

8.2 Data Handling Rules

For the analysis of serum Sirukumab concentration, the concentration values below the LLOQ (= 0.1 ug/mL) will be imputed as 0 ug/mL, and all non-missing measurements (planned and unscheduled) will be used.

8.3 Analysis Methods

8.3.1 Analysis Methods for Pharmacokinetics

For participants in PK analysis set, descriptive statistics (n, mean, SD, coefficient of variation, median, range and IQR) of serum Sirukumab concentration ($\mu\text{g/mL}$) will be tabulated over time. The PK concentrations at scheduled visits (pre- and post-dose on Day 1, Day 14, 21 and 28) will be summarized in a table.

Descriptive statistics will also be tabulated by following baseline subgroups:

- (1) By median baseline body weight (kg): \leq median, and $>$ median at baseline,
- (2) By CRS score at baseline ($\leq 3, 4, 5$),
- (3) By baseline Free IL-6 (ng/L) tertiles: $\leq 33\%$, $> 33\%$ and $\leq 66\%$, and $> 66\%$ percentiles at baseline, and
- (4) By baseline CRP (mg/L) tertiles: $\leq 33\%$, $> 33\%$ and $\leq 66\%$, and $> 66\%$ percentiles at baseline.

(Note: participants with missing baseline values of subgroup variable will not be used for the subgroup analysis.)

Following plots (Y-axis using scale of Log_{10} , and if mean of values at any visit becomes less than 0 then it will be shown as <0.01 on Y-axis) for serum Sirukumab concentration over time at scheduled visits (post- baseline on Day 1, Day 14, 21 and 28) will be generated:

- (1) Mean and SD over time,
- (2) Median and IQR over time,
- (3) Median and IQR over time by CRS score at baseline ($\leq 3, 4, 5$),
- (4) Median and IQR over time by baseline Free IL-6 (ng/L) tertiles: $\leq 33\%$, $> 33\%$ and $\leq 66\%$, and $> 66\%$ percentiles at baseline), and

(5) Median and IQR over time by baseline CRP (mg/L) tertiles: <= 33%, > 33% and <= 66%, and > 66% percentiles at baseline).

It is possible that a few participants experienced some interruptions during the infusion of the study drug. If greater than 10 subjects had dose interruption, a sensitivity analysis is planned for the participants in the PK analysis set who did not have any such interruptions. Sensitivity analysis will include the descriptive statistics (n, mean, SD, coefficient of variation, median, range and IQR) of serum Sirukumab concentration ($\mu\text{g/mL}$) over time.

If data permit, the relationships between serum Sirukumab concentrations and biomarkers or efficacy may be analyzed graphically. If any visual trend is observed, a suitable population PK/PD model may be developed to describe the exposure-response relationship. The results of the population PK/PD analysis will be presented in a separate technical report.

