9.3. Populations for Analysis Sets

For purposes of analysis, the following populations are defined:

The efficacy endpoints will be analyzed on the Intent-to-Treat (ITT) and by randomized treatment. The ITT set consists of all participants who were randomized and treated.

The primary and key secondary analyses will be tested on the participants with confirmed critical COVID-19 disease.

All safety endpoints will be evaluated on the Safety Population which consists of all randomized participants who received study intervention and will be analyzed by actual treatment.

Pharmacokinetic data will be evaluated on participants in the ITT set who received sirukumab.

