2.2.5 Pharmacokinetics (PK) Analysis Set

The PK analysis set includes all participants in the AST analysis set with no interruption of study medication and who also had at least 1 valid blood sample drawn for PK analysis after dose of Sirukumab. This analysis set will be used to analyze the PK concentration using actual treatment received by a participant (PK analysis set as Treated).

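### The planned PK sensitivity analysis excludes infusion interruptions from a set that already excludes them, so it reproduces the main PK table; the exclusion is also absent from the protocol

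*SAP*

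**What the plan says.** **The PK set.** SAP 2.2.5 states: "The PK analysis set includes all participants in the AST analysis set with no interruption of study medication". It also requires at least one valid PK sample after the sirukumab dose. SAP 8.1 repeats the definition and adds: "The PK analysis will be performed using the PK analysis set and will exclude any participant who received the Placebo".

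**The main PK output.** SAP 8.3.1 opens: "For participants in PK analysis set, descriptive statistics (n, mean, SD, coefficient of variation, median, range and IQR", with the concentrations tabulated over time. Subgroup tables and five concentration plots follow.

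**The sensitivity analysis.** The same section then says: "It is possible that a few participants experienced some interruptions during the infusion of the study drug". The trigger is: "If greater than 10 subjects had dose interruption". When it is met, "a sensitivity analysis is planned for the participants in the PK analysis set who did not have any such interruptions", with the same list of descriptive statistics over time.

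**The protocol.** Protocol 9.3 sets a different population: "Pharmacokinetic data will be evaluated on participants in the ITT set who received sirukumab". It makes no mention of interruptions.

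**The neighbouring set.** The immunogenicity (IMG) set in SAP 2.2.6 accepts full or partial sirukumab doses and has no interruption criterion.

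**The concern.** A sensitivity analysis that leaves out interrupted infusions is useful only if the main analysis contains them. Here the main set has already removed them, so the planned check cannot test whether interruptions affect the concentration summaries. The SAP provides for the case where interruptions are common, and in that case the main PK tables would describe only uninterrupted infusions, with nothing beside them to show what the omission did.

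There is also a mismatch between documents. The protocol's PK population is broader on this criterion, and the SAP narrows it without giving a reason.

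**Working it through.** The plan gives no figure to reproduce; the check is one of set membership.

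**Definitions**
- T = treated participants who received sirukumab and have at least one valid post-dose PK sample (SAP 2.2.5, 8.1).
- I = participants whose infusion was interrupted (SAP 8.3.1).

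**Step 1: main PK set.** SAP 2.2.5 and 8.1 give T minus I.

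**Step 2: sensitivity set.** SAP 8.3.1 takes members of the PK set without interruptions: (T minus I) minus I = T minus I. This is the set in Step 1.

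**Step 3: outputs.** Both analyses ask for n, mean, SD, coefficient of variation, median, range and IQR of serum concentration over time. Same participants and same statistics give the same table.

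**Step 4: is it the same event in both places?** Protocol 4.1 gives one infusion on Day 1, and Protocol 7.1 treats discontinuation of study intervention as not applicable. The exposure listing in SAP 4.4 records interruption of that infusion and its length. The SAP draws no distinction between an interruption of medication (2.2.5) and an interruption during the infusion (8.3.1).

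**Step 5: where interrupted participants do appear.**

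| Place in SAP | Interrupted participants included? |
|---|---|
| 8.3.1 main tables, subgroup tables and plots | No |
| 8.3.1 sensitivity table | No |
| 8.3.2 concentrations by antibody status (IMG set) | Yes, if they have a valid post-dose immunogenicity sample |
| 4.4 exposure listing | Yes, but this is a listing, not a summary |

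**Step 6: scale, for illustration only.** The number interrupted is not given. The smallest count that meets the trigger is 11.
- If all 11 were on sirukumab with critical disease: 11/74 = 15% of that planned arm (Protocol 9.2).
- If all 11 were on sirukumab and the roughly 100 severe participants are added, assuming a 2:1 split: (111 + 100) × 2/3 = about 141, and 11/141 = 8%.
- If the 11 are counted over both arms, assuming 2:1 allocation and equal interruption rates: 11 × 2/3 = about 7 on sirukumab, which is 7/141 = 5%.

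**The case against.** The best defence of the text is that the two sections mean different things: an incomplete dose in 2.2.5 and a temporary pause in 8.3.1. The sensitivity analysis would then have content. The SAP does not say this, however, and if it was intended the wording still needs correcting.

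A second defence is that little depends on it. The post-dose sample is timed from the end of the infusion (Protocol Schedule of Activities), later samples fall on Days 14, 21 and 28, and mean half-life at 5 mg/kg is about 21 days (Protocol 2.1.1). A short pause in a completed infusion should barely change those concentrations; an incomplete dose could. That stands, and it limits the importance of the point.

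A reader might also infer several stronger things that the documents do not support:

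- **That interrupted participants are never summarised.** Those with a valid post-dose immunogenicity sample belong to the IMG set, and 8.3.2 tabulates and plots their serum concentrations by antibody status.
- **That the exclusion is hidden.** It is stated twice, the size of each analysis set is tabulated (SAP 4.3), and interruptions are listed for each treated participant (SAP 4.4).
- **That meeting the trigger means more than 10 sirukumab participants are missing.** The trigger counts subjects without naming an arm, and placebo is also given as an infusion (Protocol 6.1).
- **That the comparison has become impossible.** The data are collected, so it could still be made. It is just not what the SAP specifies. The population PK modelling in Protocol 8.4.3 and 9.4.7 states no interruption exclusion either.

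**Conclusion.** The point holds in a limited form. As written, the sensitivity analysis in SAP 8.3.1 has the same population and statistics as the main PK table and so carries no information. Interrupted participants are absent from all 8.3.1 output, and no planned analysis sets PK with them against PK without them. Concentration tables in 8.3.1 and 8.3.2 would rest on populations that treat interruptions differently. The SAP's exclusion has no counterpart in Protocol 9.3.

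This rests on one assumption, that interruption has the same meaning in 2.2.5, 8.1 and 8.3.1. The single-infusion design supports it and nothing in the SAP contradicts it.

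The consequence is small. PK is an exploratory objective with descriptive analysis; primary, key secondary and safety conclusions are not affected. The percentages above only indicate scale and do not estimate how many participants were interrupted.

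**What to change.** Delete the no-interruption condition from SAP 2.2.5 and from its restatement in 8.1. The PK set then becomes all sirukumab-treated participants with at least one valid post-dose PK sample. Keep the 8.3.1 sensitivity analysis as it is: it would then compare the full PK set with the uninterrupted subset, which is what such an analysis is for. It would also help to state in 8.3.1 whether the trigger counts sirukumab participants only or both arms.

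This removes the departure from Protocol 9.3 on interruptions. It does not make the two populations identical: the SAP would still start from the as-treated set and require a valid sample, whereas the protocol starts from the ITT set.

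The cost is a wording change in the SAP. No new data are needed, because interruptions are already recorded.

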8.3.2 Analysis Methods for Immunogenicity

Analysis of immunogenicity information will be performed using participants in IMG analysis set.

A participant is said to be positive for antibodies to Sirukumab if participant was positive for antibodies to Sirukumab at any time after Sirukumab administration until Day 28 of the study. A participant is classified as negative for antibodies to Sirukumab only if he/she was not positive at any time through Day 28 (that means participant must be negative for antibodies all through Day 28).

For participants who had 1 or more evaluable samples obtained after Sirukumab administration through study Day 28, a table showing number and percent of participants with positive results and negative results for antibodies to Sirukumab will be generated. Number of participants with peak titers will be shown in the table.

For Day 1 (pre- and post-dose), Day 14, 21 and 28 of the study, a table with summary statistics of serum Sirukumab concentrations (n, mean, SD, coefficient of variation, median, min and max) will be provided by participants with negative and positive for antibodies to Sirukumab.

A plot showing median and IQ range of serum Sirukumab concentrations over time by antibody status will be generated. Plots showing median and IQ range of serum Sirukumab concentrations over time by antibody status will be generated by the following subgroups:

- (1) Median and IQR over time by baseline Free IL-6 (ng/L) tertiles: <= 33%, > 33% and <= 66%, and > 66% percentiles at baseline), and
- (2) Median and IQR over time by baseline CRP (mg/L) tertiles: <= 33%, > 33% and <= 66%, and > 66% percentiles at baseline).

A listing of participants positive for antibodies to Sirukumab any time through Day 28 will be generated.

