8.4.4. Immunogenicity Assessments

Antibodies to sirukumab will be evaluated in serum samples collected on Day 1 predose and on Day 28.

Serum samples will be screened for antibodies binding to sirukumab and the titer of confirmed positive samples will be reported. Other analyses may be performed to verify the stability of antibodies to sirukumab and/or further characterize the immunogenicity of sirukumab.

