9.4.7. Other Analyses

Pharmacokinetic Analyses

Serum sirukumab concentrations will be summarized using descriptive statistics. The concentrations below the lowest quantifiable sample concentration of the assay will be treated as zero in the summary statistics. All concentrations below the lowest quantifiable sample concentration of the assay or missing data will be labeled as such in the concentration data listing or statistical analysis dataset.

If feasible, population PK analysis of serum concentration-time data of sirukumab may be performed using nonlinear mixed-effects modeling. Data may be combined with other selected studies to support a relevant structural model. Available baseline participant characteristics (eg, demographics, laboratory variables) may be tested as potential covariates affecting PK parameters. The results of the population PK analysis will be presented in a separate report.

Biomarkers Analyses

Analysis of the relationship between various blood biomarkers, such as cytokines, and viral parameters, immunogenicity, safety and clinical outcome may be conducted.

Descriptive statistics for actual values and (relative) changes from baseline for the different blood biomarkers assessed, will be tabulated for each biomarker at each applicable time point specified in the [Schedule of Activities \(SoA\)](#). Statistics include n, mean, SD, geometric mean, median, minimum, and maximum.

Statistical approaches to explore correlations between clinical outcome and blood biomarkers vary and depend on the different data types of the applied technology platforms, as well as on the extent of observed differences between participants. Analyses will be conducted at the sponsor's discretion and may be reported separately from this study.

Immunogenicity Analyses

The incidence of antibodies to sirukumab will be summarized for all participants in the ITT population with appropriate samples for detection of antibodies to sirukumab (ie, participants with at least predose and the Day 28 sample obtained).

Virology Analyses

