2.2.6 Immunogenicity (IMG) Analysis set

The IMG analysis set consists of participants in AST analysis set who received a dose (full or partial) of Sirukumab during the study and have at least one valid blood sample for immunogenicity analysis after Sirukumab dose. This analysis set will be used to analyze immunogenicity using the actual treatment received by a participant (IMG analysis set as Treated).

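### Antibody positivity in SAP 8.3.2 rests on post-dose results alone, so antibodies present before dosing are counted together with those that appear after it

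*SAP*

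**What the plan says.** **Sampling.** Protocol 8.4.4 states: "Antibodies to sirukumab will be evaluated in serum samples collected on Day 1 predose and on Day 28". SAP 8.1 gives the same two times: "Serum samples to evaluate the antibodies to Sirukumab are collected on Day 1 pre-dose and on Day 28". Under the footnotes to the Schedule of Activities, participants discharged earlier have their Day 28 assessments on the day of discharge. Protocol 8.4.4 adds that "the titer of confirmed positive samples will be reported".

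**Who is counted.** Protocol 9.4.7 summarizes incidence in "participants with at least predose and the Day 28 sample obtained". The SAP's immunogenicity set (2.2.6) takes sirukumab-treated participants who "have at least one valid blood sample for immunogenicity analysis after Sirukumab dose". The SAP 8.3.2 table is introduced in matching terms: "For participants who had 1 or more evaluable samples obtained after Sirukumab administration through study Day 28". Neither SAP passage asks for a predose sample.

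**How they are classified.** Under SAP 8.3.2 a participant is positive if "positive for antibodies to Sirukumab at any time after Sirukumab administration until Day 28 of the study", and is "negative for antibodies to Sirukumab only if he/she was not positive at any time through Day 28". The resulting status then splits a table of serum sirukumab concentrations and several median and interquartile-range plots. A listing of antibody-positive participants is also planned.

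**Objective and endpoint.** Both documents place immunogenicity among the exploratory objectives and describe it as immunogenicity following treatment. The paired endpoint is the proportion of participants with antibodies at Day 28, or at discharge if that comes later.

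**The concern.** An antibody found at Day 28 may have arisen after sirukumab or may have been there already. The predose sample is what separates the two, and the SAP rule does not use it. Neither document has a baseline-positive category or a titer-rise rule for antibodies that dosing boosts. Elsewhere the SAP does refer to baseline: laboratory grades (9.2.2), vital signs (9.3.2) and ECG findings (9.4.2) are treatment-emergent only if they are worse than the baseline finding.

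Two outputs are affected. The first is the reported proportion positive, which a reader will take as the response to sirukumab because the objective concerns immunogenicity after treatment and the protocol speaks of incidence. The second is the comparison of concentrations by antibody status. There the positive group is likely to hold very few people, so one or two misallocated participants could change its content.

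**Working it through.** The plan states no sample size or expected rate for immunogenicity, so there is no figure of its own to reproduce. The check has two parts.

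**1. The rule applied to each result pattern**

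| Predose | Day 28 | Class under SAP 8.3.2 |
|---|---|---|
| negative | negative | negative |
| negative | positive | positive |
| positive | positive | positive, same row as the line above |
| positive | negative | not positive; negative only if the negative rule is read as post-dose only, otherwise unclassified |
| missing | positive | positive in the SAP; outside the protocol 9.4.7 denominator |

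The fourth line is open because the negative rule runs through Day 28 but has no stated starting point. The listing criterion has the same gap, so it could include a participant whom the table does not count as positive.

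**2. Illustration of size**

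Inputs from the documents:
- Earlier intravenous studies (protocol 2.1.1): 0/31, 0/32 and 1/20 positive. Pooled: 1/(31 + 32 + 20) = 1/83 = 1.2%.
- Planned sirukumab arm in critical disease (SAP 1.4): about 74.
- About 100 participants with severe disease already enrolled, randomized 2:1, so about 67 on sirukumab and 74 + 67 = 141 in all.

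Assumptions, not in the documents:
- t = 1/83 is the treatment-emergent rate among participants negative before dosing.
- b is the share reactive before dosing and still positive at Day 28, shown from 0 to 10%.

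Expected emergent cases if everyone were evaluable: 74/83 = 0.9, or 141/83 = 1.7.

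Proportion positive under the SAP rule = b + (1 − b)t. Emergent proportion = (1 − b)t. Share of positives already present = b / [b + (1 − b)t]. For b = 2%: 0.02 + 0.98 × 0.01205 = 0.0318, and 0.02/0.0318 = 63%.

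| b (assumed) | SAP rule, % positive | Emergent, % | Already present, % of positives | Expected persistent baseline positives in 74 |
|---|---|---|---|---|
| 0% | 1.2 | 1.2 | 0 | 0 |
| 1% | 2.2 | 1.2 | 46 | 0.7 |
| 2% | 3.2 | 1.2 | 63 | 1.5 |
| 5% | 6.1 | 1.1 | 81 | 3.7 |
| 10% | 11.1 | 1.1 | 90 | 7.4 |

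The percentages do not depend on the number of participants. The counts are upper figures. SAP 1.4 assumes 20% mortality by Day 28 on sirukumab, which is 0.20 × 74 = about 15 people, and those who die in hospital before Day 28 have no scheduled post-dose antibody sample.

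**The case against.** **The endpoint is a Day 28 proportion.** In both documents the endpoint is the proportion with antibodies at Day 28 or later discharge, and the SAP rule is a fair implementation of that. A reader might infer that the protocol requires a change from baseline. It does not say so: 9.4.7 requires a predose sample to exist but gives no rule for using its result. This stands. What remains is that 9.4.7 calls the quantity an incidence and makes the predose sample a condition, and the SAP drops that condition without explanation.

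**Not every predose-reactive participant is affected.** A reader might infer that everyone reactive before dosing is reported as having developed antibodies. The SAP says positive, not developed, and only participants also positive after dosing are counted. Nor is a confirmed pre-existing antibody a false positive; it is a real antibody in the wrong row.

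**No multiplier can be supported.** A reader might take from the table above that the reported incidence will be several times the true one. The predose rates there have no source in the documents, and zero is possible. The documents also do not say how predose results were handled in the earlier studies. If 1/83 counts all positives, a persistent baseline rate of 5% would give at most 1 positive in 83 with probability 0.95^83 + 83 × 0.05 × 0.95^82 = about 0.08. The populations differ, so this does not rule out the higher rates, but it gives them no support.

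**The consequences are small.** The outputs are descriptive, no test depends on them, and with about two positives a concentration comparison says little under either definition. The listing might show predose results, but its columns are not given in the SAP. This bears on the weight of the point; the rule still merges the two groups.

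**Conclusion.** The point holds as a minor correction. The SAP's positivity rule cannot separate antibodies present before dosing from those that appear after it. Its denominator departs from protocol 9.4.7, and one result pattern is left without a clear class. These conclusions follow from the text and need no assumption.

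The numerical effect is unknown. It is zero if no participant is persistently reactive before dosing. If the emergent rate is near the 1/83 seen earlier, about one to two emergent cases are expected, so one or two persistent baseline positives would match them. That comparison assumes that the earlier rate carries over to this population and reflects emergent antibodies, neither of which the documents establish. No primary or key secondary conclusion is affected.

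**What to change.** In SAP 8.3.2:

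- Define treatment-emergent positivity as predose negative and post-dose positive, or predose positive with a titer rise. The sponsor should prespecify the size of the rise from assay performance.
- Show participants who are baseline-positive without such a rise in their own row. This also gives a class to those positive before dosing and negative at Day 28.
- Use the treatment-emergent flag for the concentration table and plots by antibody status, and state the period that the negative rule and the listing cover.
- Restrict the incidence denominator to participants with a predose sample and a Day 28 (or discharge) sample, in line with protocol 9.4.7, and amend 2.2.6 or the table definition to match. State how a missing predose result is handled.

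If the sponsor intends a simple Day 28 prevalence, the SAP should say so, label the table accordingly and explain the departure from 9.4.7.

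The cost is SAP wording and programming. The samples are already scheduled, and titers are to be reported for confirmed positives. The downside is that participants without a predose result leave the incidence denominator; the documents do not indicate how many there will be.
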